#### 9.4.4 BASELINE DESCRIPTIVE STATISTICS

Care partners in each study group (JITAI and control) will be compared descriptively according to Consolidated Standards of Reporting Trials Guidelines.

T tests/ANOVA will be used to examine group differences for continuous variables (e.g., age, HRQOL outcomes). Chi-squared/Fisher exact tests will be used to examine group differences for categorical variables (e.g., caregiver type [SCI, HD, HCT], sex, ethnicity, race, education, marital status, relationship to care recipient).

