## 4 STUDY DESIGN

### 4.1 OVERALL DESIGN

**Study Design:** This behavioral trial will use a two-arm randomized controlled design. Each of the 60-90 care partner participants will be randomized to an active “JITAI” arm (n=10-15 care partners of SCI, n=10-15 care partners of HD, n=10-15 care partners of HCT) or to a control arm (n=10-15 care partners of SCI, n=10-15 care partners of HD, n=10-15 care partners of HCT). The random allocation of participants to the treatment arm or control arm establishes the basis for testing the statistical significance or difference between the groups.

**Randomization:** Blocked randomization will be used to limit bias and achieve an equal distribution of participants to the control and treatment arms. A randomization list will be generated for each condition (SCI, HD, HCT) and the study statistician will oversee randomization. The participant will be randomized once he/she is deemed eligible and has provided informed consent (i.e. at enrollment prior to baseline data collection). The study coordinator/research assistant who consented the participant will use the appropriate condition’s randomization list to assign the participant to the correct study arm.

**Duration of Study Participation:** Study participation for both arms of the study (control and JITAI) involves a baseline assessment, followed by an approximate 10-day run-in period then a 3-month (90 day) home monitoring period (in which the intervention will be administered to the JITAI group). Thus, the total duration of the study is ~100 days.

**Study Sites:** This is a single-site study at the University of Michigan.

**Study Intervention:** The just in time adaptive intervention (JITAI) uses sensor data derived from the Fitbit® (e.g., accelerometer-based estimates of physical activity and sleep) and real-time self-report ratings (assessed once daily) of HRQOL (caregiver strain, depression, anxiety) to deliver personalized “pushes” to participants via a study specific app (CareQOL app). The personalized pushes will be delivered on ~50% of the days over the 3-month intervention period.

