## 9.2 SAMPLE SIZE DETERMINATION

The main purpose of the current trial is to establish the feasibility and acceptability of an intensive data collection protocol in order to inform the a larger, later-stage effectiveness study on the JITAI in care partners of persons with chronic medical conditions. Thus, the current study is designed to provide a point of estimate for the effect of the JITAI for this future large-scale trial. Given that there are no formal power analysis calculations for this type of analysis, we have based the proposed sample size on our previous experience conducting these types of trials. Specifically, we believe that ~50 participants will provide sufficient numbers and diagnostic diversity to evaluate feasibility and acceptability of new mobile health apps. Thus, or sample size of N=60 caregivers (30 per arm and 20 per care partner group), exceeds this estimate and should provide a reasonable range of scores on the HRQOL outcome measures to guide later phase trial work.

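### Section 9.4.4 promises a descriptive comparison of the arms but then orders significance tests of baseline differences, including on the stratification factor; these p-values cannot measure imbalance

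*Combined protocol and SAP*

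**What the plan says.** Section 9.4.4 carries the title Baseline Descriptive Statistics and opens: "Care partners in each study group (JITAI and control) will be compared descriptively according to Consolidated Standards of Reporting Trials Guidelines". Two testing instructions follow. For continuous variables: "T tests/ANOVA will be used to examine group differences for continuous variables (e.g., age, HRQOL outcomes"). For categorical variables: "Chi-squared/Fisher exact tests will be used to examine group differences for categorical variables (e.g., caregiver type [SCI, HD, HCT], sex, ethnicity, race, education", a list that continues with marital status and relationship to the care recipient. Both lists are given as examples, so they are open. Neither Section 9.4.4 nor any other section gives a significance level, a purpose for these tests or a rule for using their results.

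Section 4.1 describes the allocation: "Blocked randomization will be used to limit bias and achieve an equal distribution of participants to the control and treatment arms", and "A randomization list will be generated for each condition (SCI, HD, HCT) and the study statistician will oversee randomization". Caregiver type is therefore the stratification factor. Section 4.1 also places randomisation after consent and before baseline data collection.

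On size, Section 9.2 gives a "sample size of N=60 caregivers (30 per arm and 20 per care partner group"), while Section 4.1 gives 60-90 participants, that is 30-45 per arm.

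**The concern.** An analyst cannot both keep to a descriptive comparison and run the tests. The word *group* most naturally means arm, because the sentence just before defines it so and because caregiver type is itself one of the tested variables.

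The p-values would help little in either direction. A small one may be a chance flag, yet it invites the reading that randomisation failed, or the later choice of that variable as a covariate. A large one may be taken as evidence of balance when the trial is too small to show that. What matters for the exploratory arm comparison in Sections 9.3 and 9.4.1 is how large an imbalance is and how strongly the variable predicts the outcome. A p-value supplies neither. Section 9.2 intends the effect estimate to inform a later trial, and Section 9.4.1 leaves that comparison as an unadjusted two-group t-test (or a nonparametric test), so covariate choice is open after the data are seen.

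**Working it through.** The plan gives no error rate, test count or power calculation for these tests, so there is no figure of its own to reproduce beyond the sample size: 3 × 20 = 2 × 30 = 60, which is consistent.

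**Inputs**
- Significance level: not stated. Assumed two-sided 0.05, with 0.01 and 0.10 as the range.
- Categorical variables: seven are named in 9.4.4. Without caregiver type, six remain.
- Continuous variables: age plus HRQOL outcomes. Narrow reading: the 3 exploratory outcomes in Section 3 (strain, depression, anxiety). Full reading: the 14 baseline scores in Section 8.1.5 (11 T-scored measures, 2 Global Health scores, 1 COVID item).
- Test counts: narrow 1 + 3 + 6 = 10; full 1 + 14 + 6 = 21.
- Arm size: 30 (Section 9.2) to 45 (upper end of Section 4.1).

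**Chance flags.** With k independent tests at level α, P(at least one) = 1 − (1 − α)^k, and the expected number is kα.

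| α | k = 10 | k = 21 |
|---|---|---|
| 0.01 | 9.6% | 19.0% |
| 0.05 | 40.1% (expected 0.50) | 65.9% (expected 1.05) |
| 0.10 | 65.1% | 89.1% |

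At 0.05 the probability first passes one half at k = 14 (1 − 0.95^14 = 0.512).

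The HRQOL scales overlap, so independence overstates these figures. A simulation (3,000 replicates per setting, 30 and 45 per arm, assumed HRQOL inter-correlations from 0 to 0.7, assumed category shares) gave 34-40% for 10 tests and 43-63% for 21. Combined with the independence formula, the ranges at 0.05 are about 34-40% and 43-66%.

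**The stratification factor.** Pearson chi-squared on the 2 × 3 table of arm by condition:
- Complete blocks (10/10 or 15/15 in each condition): chi-squared = 0, p = 1.00.
- 20 per condition, arms differing by 2 in every condition, worst pattern (11, 11, 9) against (9, 9, 11): expected counts are 31/3 = 10.33 and 29/3 = 9.67. The squared deviations sum to 2 × 0.667² + 1.333² = 2.667 in each row. Chi-squared = 2.667/10.33 + 2.667/9.67 = 0.534 on 2 degrees of freedom, p = 0.77.
- The same with a difference of 4: (12, 12, 8) against (8, 8, 12) gives 10.667/10.667 + 10.667/9.333 = 2.143, p = 0.34.

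The block size is not stated, so the differences of 2 and 4 are illustrations. This test adds essentially no chance flags, which is why it is left out of the counts. It is uninformative because the design has already fixed its answer.

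**What a non-significant t-test excludes.** The smallest significant standardised difference is t(0.975, 2n − 2) × √(2/n):
- n = 30: 2.00 × √(2/30) = 0.52 SD
- n = 45: 1.99 × √(2/45) = 0.42 SD

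If the sample SD equals the reference value of 10 for the T metric, that is about 5.2 and 4.2 points. Any smaller observed imbalance would be reported as non-significant.

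**The case against.** **Chance flags.** A reader might infer that they are more likely than not. For example, 22 variables at 5% give 1 − 0.95^22 = 68%. The documents do not support that as a headline. Section 9.4.4 does not list 22 variables or say that every HRQOL score is tested; no level is stated; the count includes caregiver type, which cannot realistically flag; and independence is assumed across related scales. At 0.05, more likely than not holds only on the longer list, and not at the strongest correlation tried.

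**Meaning of a difference.** A reader might also infer that any baseline difference is pure chance, so the tests address a null known to be true. That is too strong here. Section 4.1 puts randomisation before baseline data collection and has the staff member who took consent use the list. Section 6.2 terminates participants who fail the run-in, and Section 7.1 replaces randomised participants who drop out. Knowledge of allocation or selection could therefore produce a real difference. This stands, but it does not rescue the tests: the plan gives them no such purpose, and at 30-45 per arm a p-value cannot tell these causes from chance.

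**Size of undetected imbalance.** A 0.5 SD imbalance escapes significance at 30 per arm (0.52) but not at 45 (0.42), so it cannot be stated as a general property of the trial.

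**Consequences.** No section uses baseline p-values to judge randomisation or to choose covariates. The primary endpoint is item frequencies in the full sample, and the secondary endpoints are descriptive. This stands and limits the importance of the point. Stating the purpose and comparison groups of the tests would also remove the contradiction, and *ANOVA* leaves some room for a three-condition comparison. If that was meant, the text still needs to say so.

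**Conclusion.** The contradiction in Section 9.4.4 is certain on the natural reading of *group* as arm. The test of caregiver type is settled by the design. The chance-flag figures (34-40% for 10 tests, 43-66% for 21) rest on an assumed level of 0.05, on the two readings of the variable list, and on assumed correlations and category shares. The detection limits (0.52 and 0.42 SD) rest on the same level and on equal arms of 30 and 45.

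The documents do not show that a flag is probable on every reading, that a flagged difference is meaningless, or that any planned result depends on these p-values. The consequence is confined to the baseline table and to the room it leaves for covariate choice in the exploratory comparison. It is worth correcting because the change is small, but it does not threaten the trial's main conclusions.

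**What to change.** In Section 9.4.4:
- Delete the significance tests between JITAI and control. Report mean (SD) or n (%) by arm with the size of the difference, for example a standardised difference.
- Keep ANOVA and chi-squared tests only to describe the three non-randomised diagnosis groups, and label them so.

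In Section 9.4.1:
- Specify in advance that the exploratory JITAI-control comparison of HRQOL is adjusted for baseline score and condition, and that no covariate is chosen from baseline p-values.

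The cost is a few sentences, fewer tests in the baseline table and slightly more modelling for the exploratory comparison. No new data are needed, since baseline scores are already collected and condition is already used to randomise. There is one drawback: as planned, the baseline score is measured after allocation and could be influenced by it. Either collect baseline data before allocation is disclosed, or state this as a limitation of the adjusted estimate.

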## 10 SUPPORTING DOCUMENTATION AND OPERATIONAL CONSIDERATIONS

### 10.1 REGULATORY, ETHICAL, AND STUDY OVERSIGHT CONSIDERATIONS

#### 10.1.1 INFORMED CONSENT PROCESS

##### 10.1.1.1 CONSENT/ASSENT AND OTHER INFORMATIONAL DOCUMENTS PROVIDED TO PARTICIPANTS

The participant will be provided with a PDF of their certified consent form approved by the U-M IRBMED describing in detail the study intervention, study procedures, and risks. Informed consent will be obtained prior to the participant completing any study-related assessments. An example can be found in the U-M IRBMED application for this study.

##### 10.1.1.2 CONSENT PROCEDURES AND DOCUMENTATION

All consent procedures will be approved by the U-M IRBMED. Informed consent will be conducted virtually (e.g., Zoom, Bluejeans, telephone, etc.). Consent will be documented using the REDCap consent platform; participants will indicate their consent by entering their name and the date into the REDCap consent document. All individuals who are interested in participating in the study will be encouraged to ask questions about the study and their participation, and will be given as much time as needed to make a decision about participating. Participants will receive a pdf copy of their 'signed' consent.

Participants completing the optional semi-structured interview portion of the study (see section 8.1.6) will consent for this portion of the study using a separate consent form, following the same procedures above.

A waiver of informed consent and HIPAA waiver is requested for eligibility screening for this study and for collection of medical record data for the individual that the participant (care partner) is caring for. The medical record data is needed to accurately capture date of diagnosis, details of diagnosis, disease stage/severity, etc.

#### 10.1.2 CONFIDENTIALITY AND PRIVACY

Participant confidentiality and privacy is strictly held in trust by the participating investigators, their staff and the funder. This confidentiality is extended to the data being collected as part of this study. Data that could be used to identify a specific study participant will be held in strict confidence within the research team.

All research activities will be conducted in as private a setting as possible. The study participant's contact information will be securely stored for internal use during the study. Study staff will keep a master list of their participant names and matching participant IDs. This master list will not be shared outside of the study team, and will be kept by study personnel in a password-protected file on a secure server or in a secure environment (e.g., locked cabinet, restricted access). No one other than the study

team will have access to their master list. Informed consents will be stored in a study-specific database which contains only the informed consents. At the end of the study, all records will continue to be kept in a secure location for as long a period as dictated by the U-M IRBMED and Institutional policies.

No personal identifying information will appear on or with the participant data, where possible. Each participant will be assigned a participant ID by the study team to maintain confidentiality. The primary unique identifier is the study-assigned participant ID. The participant's self-report data and CRF data will be identified with the participant ID. Additionally, an access code will be assigned to each participant which they will use to enroll in the CareQOL app. Participants will register their study Fitbit® on the Fitbit® app using a username and email address of their choice. The data collected on the Fitbit® will be linked to the CareQOL app by user authentication token, which is comprised of a random series of characters that is used to securely query for user activity data; no identifying information (including email address or Fitbit® user ID) is saved in the CareQOL app.

For participants completing the optional semi-structured interview portion of the study (see section 8.1.6), no personal identifiers will be kept with the transcription of the interview. Only audio will be recorded during the interview (no video), and the participant will be instructed and reminded (if needed) to avoid using names, other identifiers, etc. during the interview. Audio-recordings and transcripts will be stored securely (e.g., password protected server, study-specific M-Box).

The study data entry and study management systems (e.g., CareQOL app, REDCap, Qualtrics, M-Box, Fitbit®, etc.) used in the study are secured and password protected. At the end of the study, all study databases will be de-identified and archived securely at the University of Michigan.

#### Measures Taken to Ensure Confidentiality of Data Shared

The PI will ensure all mechanisms used to share data will include proper plans and safeguards for the protection of privacy, confidentiality, and security for data dissemination and reuse (e.g., all data will be thoroughly de-identified and will not be traceable to a specific study participant).

---

#### 10.1.3 FUTURE USE OF STORED SPECIMENS AND DATA

##### Data Retention

Research data and information will be retained for both study record-keeping purposes and for future research use. Any materials with identifiers (e.g., informed consents) will be stored in locked filing cabinet or on a secure server separate from coded study information.

Data from participants who withdraw from the study will be retained in the study database.

##### Study Record Keeping

During the study, we will maintain identifiable data to facilitate day-to-day study operations such as follow-up contact, distribution of study incentives, etc. These records may be destroyed after 7 years per U-M record keeping guidelines (<https://az.research.umich.edu/medschool/guidance/record-keeping-guidelines>).

##### Data for Future Research Use

We will archive de-identified data for future research use. These data may be used for additional analyses related to the main study, new analyses, and in grant proposals for new research.

- The data will be stored on Michigan Medicine servers in a HIPAA-compliant electronic data capture system and/or statistical datasets that are stripped of identifiers.
- Access to the data will be at the discretion of the PIs.
- Any data shared with collaborators and other researchers will be transferred using secure methods (e.g. MiShare, encryption, etc.)

#### 10.1.4 SAFETY OVERSIGHT

The study investigators will be responsible for monitoring the data quality and safety for this study. No human subject activities will occur until U-M IRBMED approval is received.

[name] (administrative PI) will supervise the conduct of the study team and ensure that all relevant U-M IRBMED policies and procedures are following by the study team. These include: (1) All participants will provide informed consent before participating; (2) All participants will be notified of their right to withdraw or refuse to answer questions; (4) Identifying information, where possible, will be kept separate from the coded participant data; (5) All identifying information will be kept securely at all times (e.g., password protected, limited access, secure environment); (6) Participants will be informed in the consent form on how to contact the study team and IRBMED with any questions and/or concerns; and (7) Adverse events, unanticipated problems and ORIOS are reported to the U-M IRBMED per the study reporting plan.

#### 10.1.5 QUALITY ASSURANCE AND QUALITY CONTROL

QA and QC practices will be the responsibility of all team members. Training and regular meetings will be conducted to monitor and facilitate quality data collection.

##### **Training:**

All study staff will be trained on the project protocol, project data collection systems and other study-related topics prior to beginning data collection. Additionally, the project manager, in cooperation with the study PIs, will develop a manual of procedures, case report forms and other related study materials. The manual of procedures will provide step-by-step instructions on the conduct of the trial, including how to use and troubleshoot the data collection platforms. The manual of procedures and other study documents will be reviewed in detail with the study coordinators as part of the training, and all materials will be available on the study-specific shared MBox site for access at any time. Study staff will be encouraged to use the step-by-step instructions when conducting participant visits to ensure that they are adhering to the study protocol. Ongoing training will occur via regular conference. Additionally, any staff who join the team after the project starts will be required to complete the standardized training prior to enrolling participants. Training will be documented in the electronic regulatory binder.

##### **Meetings:**

- **Study Kickoff/Training** – A study kickoff and training meeting will be held prior to the start of project recruitment.

- **Investigator Meetings** – Meetings with the study investigators will be held monthly to discuss study activities, progress and troubleshoot any issues. Other project staff will attend as needed.
- **Project Staff Meetings** – The Project Manager will hold monthly meetings with the project staff after recruitment begins. These meetings will be focused on tracking recruitment efforts, data collection (including data management and clearing of queries), and discussion of protocol deviations, unanticipated problems or adverse events. Investigators may attend as needed.

---

## 10.1.6 DATA HANDLING AND RECORD KEEPING

### 10.1.6.1 DATA COLLECTION AND MANAGEMENT RESPONSIBILITIES

This project uses multiple electronic data capture and management platforms (e.g., REDCap, CareQOL, Qualtrics, Fitbit®, U-M server, Google Cloud, AWS Cloud). All platforms are designed for human subjects research and comply with federal and local data and information security practices.

Data collection is the responsibility of the study coordinators/research staff under the direction of the Project Manager and [name] (HD and SCI)/[name] (HCT). All data are entered or captured on the platforms by study staff or directly by participants (e.g. sleep/activity data, daily EMAs etc.). Any study documents completed on paper will be completed legibly and in ink.

The Project Manager and [name] will directly oversee the QA/QC activities using standard operating procedures, checklists, and built-in and study-specific data validation rules to uphold data integrity. Routine data backups will be part of this process.

The Project Manager, in cooperation with other study team members, will be responsible for setting up, monitoring and maintaining the data collection systems, and the initial implementation checks of data quality. Initially, data from the mobile app will be reviewed following the run-in period from the first 5 participants to ensure that daily data is being appropriately collected. We will continue to monitor the same 5 participants throughout the completion of the study. We will evaluate procedures to ensure that data transfers at all points are accurate. Review of the data quality will be conducted by the study statistician and PI. Irregularities or problems detected will be discussed with the study team and addressed. Following any needed adjustments or corrections to study procedures, subsequent data quality as described above will be monitored for the next 5 participants and then by random inspection of the data independently by the statistician and PI. Quarterly audits will confirm proper data transfers and downloads, and include checks for missing and/or out-of-range data, logic errors, etc. Quality control and reliability of the data will be discussed at regular team meetings.

---

